10.3 Populations for Analyses

The historical control arm will consist of patients with tissue-based diagnosis of Grade II or III astrocytomas, 18 years or older, of both genders, after surgery or biopsy followed by radiation therapy with concurrent temozolomide. As described above, these patients will have received standard treatment and would have met first tier inclusion/exclusion criteria for the study. Data for these patients will be collected via chart review. Contemporaneous controls will also consist of patients who qualify for the trial and receive standard treatment but decide not to proceed with the Optune experimental treatment because of personal preference. This personal preference must be non-medical in nature. Based on clinical experience, most commonly this non-medical patient personal preference preventing Optune use will be unwillingness to shave his/her head and/or unwillingness to wear a visible medical device on his/her head most of the day.

The interventional patient population will consist of patients with tissue-based diagnosis of Grade II or III astrocytomas, 18 years or older, of both genders after surgery or biopsy followed by radiation therapy with concurrent temozolomide and subsequent TTFields therapy plus temozolomide.

10.4 Safety Analyses

Clinical and laboratory test parameters monitored for the purpose of identifying severe adverse events (SAEs) will be summarized at the end of the trial using standard summary statistics and confidence intervals. The cumulative incidence of SAEs will be monitored continuously within the framework of a stopping rule.

Stopping Rule: We will use separate sequential Pocock-type boundaries [82] to monitor continuously for chemotherapy-related and device-related SAEs. If the cumulative number of patients experiencing an SAE is equal to or exceeds the relevant boundary indexed by the number of patients currently enrolled, a halt in enrollment will be triggered for further evaluation, to determine if the study should be discontinued for safety reasons.

The maximum acceptable toxicity rate will be set at 25% for device-related SAEs, and 50% for chemotherapy-related SAEs.

Each type of SAE will have its own boundary, which will be specified so that the overall probability of stopping the trial early for each type of SAE is 0.05 when the true device-related rate is less than 25% or the true chemotherapy-related rate is less than 50%.

TABLE 11: POCOCK BOUNDARY STOPPING RULE FOR DEVICE-RELATED SAE MONITORING

(SAE target rate=25%, N=90 patients in the treatment arm)

Number of Patients	1	2	3	4	5	6	7	8	9	10	11	12	13	14	15	16	17	18	19	20
SAE Boundary	-	-	-	4	5	5	6	6	7	7	7	8	8	9	9	9	10	10	10	11
Number of Patients	21	22	23	24	25	26	27	28	29	30	31	32	33	34	35	36	37	38	39	40
SAE Boundary	11	11	12	12	13	13	13	14	14	14	15	15	15	16	16	16	17	17	17	18
Number of Patients	41	42	43	44	45	46	47	48	49	50	51	52	53	54	55	56	57	58	59	60
SAE Boundary	18	18	19	19	19	20	20	20	21	21	21	22	22	22	23	23	23	23	24	24
Number of Patients	61	62	63	64	65	66	67	68	69	70	71	72	73	74	75	76	77	78	79	80
SAE Boundary	24	25	25	25	26	26	26	27	27	27	28	28	28	28	29	29	29	30	30	30
Number of Patients	81	82	83	84	85	86	87	88	89	90										
SAE Boundary	31	31	31	32	32	32	32	33	33	33										

(Stop trial if cumulative number of patients experiencing a device-related SAE is equal to or exceeds the SAE event boundary)

TABLE 12. POCOCK BOUNDARY STOPPING RULE FOR CHEMOTHERAPY-RELATED SAE MONITORING

(SAE target rate=50%, N=90 patients in the treatment arm; will be expanded to include contemporaneous controls if enrolled)

Number of Patients	1	2	3	4	5	6	7	8	9	10	11	12	13	14	15	16	17	18	19	20
SAE Boundary	-	-	-	-	-	-	7	8	9	10	10	11	12	12	13	14	14	15	15	16

Number of Patients	21	22	23	24	25	26	27	28	29	30	31	32	33	34	35	36	37	38	39	40
SAE Boundary	17	17	18	19	19	20	20	21	22	22	23	23	24	25	25	26	27	27	28	28

Number of Patients	41	42	43	44	45	46	47	48	49	50	51	52	53	54	55	56	57	58	59	60
SAE Boundary	29	29	30	31	31	32	32	33	34	34	35	35	36	36	37	38	38	39	39	40

Number of Patients	61	62	63	64	65	66	67	68	69	70	71	72	73	74	75	76	77	78	79	80
SAE Boundary	41	41	42	42	43	43	44	45	45	46	46	47	47	48	49	49	50	50	51	51

Number of Patients	81	82	83	84	85	86	87	88	89	90
SAE Boundary	52	52	53	54	54	55	55	56	56	57

(Stop trial if cumulative number of patients experiencing a device-related SAE is equal to or exceeds the SAE event boundary)

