6.1.2.6 Optune (TTFIELDS) + temozolomide

Optune treatment will be initiated in an outpatient clinic by the investigator's team at each center or at home by Novocure's device support specialists (DSS). 3D mapping of tumors using the FDA-approved NovoTAL software will be completed by a NovoTAL-certified treating physician or by Novocure. Scalp shaving, array placement and all device support services (including patients' and families' education of device operation, downloading and processing of technical and compliance data, and troubleshooting device malfunction) will be provided by the DSS for the first placement. Patients and/or their caregivers will continue treatment at home after being trained in device use with the support of DSS as needed.

TTFIELDS will start within 2 weeks of the first cycle of adjuvant temozolomide but must be within 7 weeks after end of temozolomide/RT. Adjuvant Temozolomide will continue for a minimum of 6 and a maximum of 12 cycles. Optune will continue for a maximum of 2 years. At first progression, patients will be allowed to continue with TTFIELDS therapy with any other therapy per standard of care. Patients will receive up to 12 one-month courses of continuous Optune treatment together with standard adjuvant temozolomide. The decision to add each additional treatment course will depend on the lack of treatment related serious adverse events which reappear upon re-challenge and lack of clinical disease progression. All technical aspects of the Optune device are handled by the DSS.

During Optune treatment the patient will be permitted to interrupt treatment for personal needs with the goal of achieving approximately 75% of the time over each 4-week period. Compliance reports with TTFIELDS will be obtained by Novocure's DSS per usual clinical treatment procedures. If a patient's compliance is below 75% of the time over any 4-week period, the patient will be trained on the importance of compliance and any barriers to compliance will be addressed by the DSS. If a patient's compliance is below 50% of the time over any 4-week period, the patient will be trained on the importance of compliance and any barriers to compliance will be addressed by the DSS and study staff.

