7.2 Procedures for Orderly Termination of Participation

Participants are free to withdraw from participation in the study at any time upon request.

An investigator may discontinue or withdraw a participant from the study for the following reasons:

- The investigator may remove a patient from the study in case of not complying with study protocol.
- If any clinical adverse event (AE), including a laboratory abnormality, or other medical condition or situation occurs such that continued participation in the study would not be in the best interest of the participant

The reason for participant discontinuation or withdrawal from the study will be recorded on the electronic Case Report Form (eCRF). Subjects who sign the informed consent form and do not receive the study intervention may be replaced. Subjects who sign the informed consent form, and receive the study intervention, and subsequently withdraw, or are withdrawn or discontinued from the study, will not be replaced.

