6. KPS
7. Summary of Adjuvant Chemotherapy (TMZ dates, number of cycles)
8. Summary of Additional Therapies (therapy types, dates, number of cycles)
9. Date(s) of Progression
10. Date of Death (if applicable)
11. Tumor tissue samples (optional)

Tumor Tissue samples are optional for control cohort patients. Adverse Events are not collected, and not reportable for control patients. MRI Correlative Study does not include control cohort participants. Concomitant Medications will not be maintained for control patients, although applicable steroid doses may be recorded as part of the RANO form.

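### The SAE stopping boundaries are read at patients enrolled, but the tables assume every counted patient's SAE status is known, so the rule halts later and less often than the tables imply

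*Combined protocol and SAP*

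**What the plan says.** Section 10.4 sets separate Pocock-type boundaries for device-related and chemotherapy-related SAEs, monitored continuously. The cumulative number of patients with an SAE is compared with the boundary "indexed by the number of patients currently enrolled". Reaching it halts enrolment for an evaluation "to determine if the study should be discontinued for safety reasons". The boundaries are specified so that "the overall probability of stopping the trial early for each type of SAE is 0.05" when the true rate is below 25% (device) or 50% (chemotherapy).

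Table 11 is headed "SAE target rate=25%, N=90 patients in the treatment arm". Table 12 uses 50% and the same N, and adds that it "will be expanded to include contemporaneous controls if enrolled". Section 9.5 says: "Adverse Events are not collected, and not reportable for control patients".

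On exposure, Section 6.1.2.6 says "Optune will continue for a maximum of 2 years", with 6 to 12 cycles of adjuvant temozolomide. Section 8.3.5 collects events from the start of study treatment until 30 days after the post-treatment visit. Section 10.1 assumes 2.5 patients per month for 36 months. Section 10.4 defines no SAE observation window, no evaluable denominator and no rule for patients still early in follow-up.

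**The concern.** A patient moves the index up by one on the day of enrolment but can add to the SAE count only later. At any look the count is incomplete while the index is not, so the rule compares a partial numerator with a full denominator. The direction needs no assumption about timing, because the observed count can never exceed its eventual value.

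The only automatic action on crossing is to halt enrolment. Once the last patient is in, a crossing can prompt an evaluation but can no longer limit how many patients are exposed. If the true SAE rate is well above the stated maximum, more patients start treatment before the rule responds, or it does not respond in time.

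**Working it through.** **Inputs.** Boundaries from Tables 11 and 12; limits 25% and 50%, N = 90 (Section 10.4); accrual 2.5 per month (Section 10.1). *Assumed, because the documents are silent:* the SAE onset distribution, and true rates of 40% or 50% (device) and 65% (chemotherapy) as examples above the limits.

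**1. Reproduce the plan's 0.05.** Let f(n,k) be the probability of k SAEs among the first n patients without an earlier crossing, and b(n) the printed boundary. Then f(n,k) = (1−p)·f(n−1,k) + p·f(n−1,k−1). At each n, the mass with k ≥ b(n) is removed and added to the stopping probability. This treats each patient's status as known when that patient is counted.

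- Device, p = 0.25: 0.0486. Chemotherapy, p = 0.50: 0.0500.
- Taking the largest constant pointwise level with overall probability at most 0.05 reproduces all 90 entries of both tables. That is how they were built.
- Device, p = 0.40: 0.846 by n = 90 and 0.839 by n = 89. Chemotherapy, p = 0.65: 0.791.

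**2. Why the index matters, by hand.** With onset uniform over w months, about 2.5·w enrolled patients are still within the window, and on average half of their eventual SAEs are unseen. The shortfall is 2.5·w·p/2. At p = 0.40 and n = 60 the eventual count averages 0.40 × 60 = 24, and the Table 11 boundary at 60 is also 24. For w = 6 the shortfall is 2.5 × 6 × 0.40 / 2 = 3, so the average observed count is 21. For w = 12 it is 24 − 6 = 18.

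**3. Simulation.** 8,000 enrolments per scenario, Poisson accrual at 2.5 per month, N = 90, standard error at most 0.006. The proposed reading is the one set out under the fix.

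Device, true rate 40%:

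| Onset uniform over (months) | Halt before enrolment ends, as written | Same, proposed | Ever crosses, as written | Mean enrolled at halt, as written | Same, proposed |
|---|---|---|---|---|---|
| status immediate | 0.84 | 0.84 | 0.85 | 38 | 38 |
| 1 | 0.82 | 0.84 | 0.83 | 41 | 39 |
| 3 | 0.75 | 0.82 | 0.81 | 48 | 41 |
| 6 | 0.63 | 0.79 | 0.78 | 56 | 45 |
| 12 | 0.35 | 0.73 | 0.78 | 68 | 53 |
| 24 | 0.04 | 0.53 | 0.78 | 80 | 67 |

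The mean-enrolled columns cover only trials that halted before enrolment ended, so each row compares different subsets of trials.

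- Other timings, device 40%, as written against proposed: fixed lag of 1/3/6 months, 0.79/0.64/0.37 against 0.83/0.81/0.76. Front-loaded onset (truncated exponential, scale one quarter of the maximum) with a maximum of 12/24 months, 0.65/0.39 against 0.78/0.70.
- Device 50%, onset over 1/3/6/12/24 months: 1.00/0.99/0.98/0.89/0.32 against 1.00/1.00/1.00/0.99/0.90.
- Chemotherapy 65%, onset over 1/3/6/12 months: 0.75/0.66/0.44/0.11 against 0.78/0.77/0.73/0.64; immediate status gives 0.79.
- Device 25%, chance of ever crossing as written: 0.04/0.02/0.01/0.01/0.01.

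**4. Table length.** Both tables stop at 90. Sections 1.1, 2.1.3.3 and 4.1.2 give 100, or up to 100, interventional patients. With the 10 to 30 contemporaneous controls expected in Section 10.1, Table 12 could need N = 90 + 10 = 100 up to 100 + 30 = 130.

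**The case against.** The plan promises only a cap on false halts, and that cap is respected. It states no power at 40% or 65%. The largest losses need slow onset, which attrition makes less likely: the assumed control median survival is 22 months, temozolomide stops at radiological progression and the device stops by second progression. With onset within 1 to 3 months, the device figure at 40% falls only from 0.84 to 0.82 or 0.75. Near the limit the design has little power under any indexing: with immediate status, a true device rate of 30% crosses with probability 0.21, and 35% with 0.54. At 50% the rule as written still halts in time with probability 0.98 or more for onset up to 6 months. SAE reporting within 24 hours, committee reporting within 5 days, DSMB review and suspension for unacceptable risk need no boundary.

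The repair can also halt on an early cluster. Device SAEs in each of the first four patients would halt the trial even with 60 enrolled, where the boundary is 24. An alternative is to index by patients who have completed a defined SAE window. The full device collection period is about 26 months, however, which leaves roughly (36 − 26) × 2.5 = 25 evaluable patients when accrual ends. A shorter window would have to be chosen and justified.

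All of this bears on size and on the choice of repair. None of it makes the enrolled-patient index match the tables, and front-loaded onset over up to 12 months still lowers 0.84 to 0.65.

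**Conclusion.** The concern holds. The tables deliver their stated level only when each counted patient's SAE status is known, and Section 10.4 reads them on another basis. The rule is conservative on false halts (about 0.01 to 0.04 at a 25% device rate) and correspondingly less protective. At a true device rate of 40%, the chance of a timely halt falls from 0.84 to 0.82 if onset is within a month, to 0.63 over 6 months and to 0.35 over 12. That later halts and fewer halts follow is certain. The size rests on the assumed onset timing, accrual of 2.5 per month and N = 90. Because other safety oversight remains and a late crossing still prompts evaluation, this should be corrected but does not invalidate the trial.

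**What to change.** 1. Replace the indexing phrase in Section 10.4 with: *enrolment halts if, for any n up to the number of treated interventional patients enrolled so far, the first n of them in enrolment order include at least as many patients with a reported SAE of that type as the boundary at n.* Every SAE counts when reported. Patients replaced under Section 7.2 ("Subjects who sign the informed consent form and do not receive the study intervention may be replaced") are not counted. A crossing on partial data is also a crossing on final data, and final data are eventually seen, so the level is 0.0486 and 0.0500 whatever the timing. With the printed tables the rule cannot halt later than the present one, because current enrolment is one of the n checked; no simulated path did.
2. Reconcile 90 and 100 interventional patients throughout. If 100 stands, regenerate Table 11: entries 91 to 100 are 34, 34, 34, 35, 35, 35, 36, 36, 36, 36, and the entry at 22 changes from 11 to 12 (level 0.0499).
3. Reconcile Table 12's control clause with Section 9.5, state who is counted, and regenerate for that N. The final boundary is 63, 68, 74 or 80 for N = 100, 110, 120 or 130.
4. Reconcile Table 12's footnote, which names device-related SAEs, with its title. State the relatedness threshold, and align the *severe* of Section 10.4 with the *serious* of Section 8.3.2.
5. Report operating characteristics for two or three assumed onset timings.

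**Cost.** At N = 90 this is a wording change: limits and table entries stay. For larger N, Table 11 needs ten new entries and one changed. Table 12 needs 10 to 40 new and 5 to 20 changed. The changed entries rise, so the no-later-halt guarantee applies only to the printed tables. Keeping controls in Table 12 would require collecting their SAEs. False halts rise to the planned 0.05. Some would come from early clusters while the crude rate among all enrolled is below the limit: about 0/0/1/14/56% of device false halts for onset over 1/3/6/12/24 months, and 9% and 53% of chemotherapy false halts at 6 and 12 months. Each SAE must be checked against an enrolment-ordered list.

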Study Population: Patients with tissue-based diagnosis of high-risk Grade II or III astrocytomas, 18 years or older, of both genders after surgery or biopsy followed by radiation therapy with concurrent temozolomide.

Phase: 2

Description of Sites/Facilities Enrolling Participants: This study is being conducted in a consortium of 10-20 high volume brain tumor centers in the U.S.

Description of Study Intervention: Treatment with TTFields (Optune®) with Adjuvant Temozolomide: TT Fields are applied through surface transducer arrays placed directly on the shaved head. Temozolomide is available in either tablet or IV infusion.

Study Duration: 60 months: 36 months enrollment plus 24 months follow-up/study completion

Accrual Goal: 100 interventional subjects and up to 100 historical and contemporaneous control subjects

Participant Duration: 24 months (study treatment) plus follow-up until death or until the study is complete/terminates.

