4.1.2 Description

This is a phase 2, multi-institutional, open-label, historically controlled, study of 100 patients with newly diagnosed high-risk Grade II and III astrocytoma combining TTFIELDS with adjuvant temozolomide compared to historical and contemporaneous controls after the completion of definitive chemoradiotherapy. The primary endpoint will be overall survival. This high-risk astrocytoma subgroup constitutes approximately 10% of all Grade II and III gliomas (Fig. 6). Therefore, in order to achieve targeted accrual goals, this study is being conducted in a consortium of 10-20 high volume brain tumor centers in the U.S.

[figure not shown]

Figure 6 Prevalence of TERT Promoter Mutation in Grade II and III Glioma. (Adapted from Eckel-Passow JE et al. *N Engl J Med* 2015;372: 2499-2508).

4.1.3 The 2016 World Health Organization (WHO) Classification of Grade II and III gliomas

This new classification provides extensive updates to the previous version from 2007 [77]. For WHO grade II and III gliomas, astrocytomas are now defined by the absence of 1p19q codeletions as determined by FISH, while oligodendrogliomas are defined by the presence of 1p19q codeletions AND IDH1/2 mutation as determined by next generation sequencing (NGS). The concordance rate between 1p19q codeletions and IDH1/2 mutation is extremely high. Gliomas with 1p19q codeletions and without IDH1/2 mutation represents an exceedingly rare entity. In fact, in the Eckel-Passow et al. study, of the 1087 infiltrating gliomas, Pisapia found no case with whole arm 1p19q codeletions was associated with wild-type IDH1/2 [18, 78]. Even when partial arm deletions were included, only 0.3% of cases with partial deletions of 1p19q was without IDH1/2 mutation [18, 78]. In fact, per WHO guidelines, oligodendrogliomas should not be diagnosed in the absence of IDH1/2 mutation (and/or 1p19q codeletions) regardless of histologic appearance since the lack of IDH1/2 mutation is equivalent to the absence of 1p19q codeletions. Thus, the absence of IDH1/2 mutation is mutually exclusive of 1p19q codeletions in the vast majority of cases. Therefore, for the purpose of this study, WHO grade II and III gliomas without IDH1/2 mutation as determined by NGS (rare variants of unknown significance are excluded and not considered to be pathologic mutations) will be considered to also have intact 1p19q (i.e. without codeletions) and a FISH test to determine 1p19q codeletions status will not be required.

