8.3.5 Time Period and Frequency for Event Assessment and Follow-Up

The occurrence of an adverse event (AE) or serious adverse event (SAE) may come to the attention of study personnel during study visits and interviews of a study participant presenting for medical care, or upon review by a study monitor.

Any medical condition that is present at the time that the participant is screened will be considered as baseline and not reported as an AE. However, if the study participant's condition deteriorates at any time during the study, it will be recorded as an AE.

Changes in the severity of an AE will be documented to allow an assessment of the duration of the event at each level of severity to be performed. AEs characterized as intermittent require documentation of onset and duration of each episode.

Study Staff will record all reportable events with start dates occurring any time after the start of study treatment for 30 days after the After Treatment Stop Visit. At each study visit, the investigator or his/her designee will inquire about the occurrence of AE/SAEs since the last visit. Events will be followed for outcome information until resolution or stabilization.

During Survival Follow-up, AEs and SAEs will not be collected. Only Progression status and survival outcomes will be monitored during this stage of the study.

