10 STATISTICAL CONSIDERATIONS

10.1 Statistical Hypotheses

- Primary Efficacy Endpoint: overall survival (OS)

Control arm: the control arm will consist of both historical and contemporaneous control patients. Historical controls will consist of TERT mutation-only astrocytoma patients treated and followed by the participating sites between January 1, 2016 and May 20, 2019. As described above, these patients will have received standard treatment and would have met first tier inclusion/exclusion criteria for the study. Data for these patients will be collected via chart review. Contemporaneous controls will also consist of patients who qualify for the trial and receive standard treatment but decide not to proceed with the Optune experimental treatment because of personal preference. This personal preference must be non-medical in nature. Based on clinical experience, most commonly this non-medical patient personal preference preventing Optune use will be unwillingness to shave his/her head and/or unwillingness to wear a visible medical device on his/her head most of the day.

- N = 90 patients total in an expected mixture ranging between 80 historical controls and 10 contemporaneous controls to 60 historical controls and 30 contemporaneous controls.
- Assumed median survival = 22 months (based on Figure 3A in Eckel-Passow et al [12])
- Follow-up = up to 60 months for the historical controls, up to 60 months for the contemporaneous controls

Experimental treatment arm: TERT mutation-only astrocytoma patients who will receive standard treatment plus TFields therapy at one of 15 participating centers.

- N = 90 patients

- Assumed accrual rate = 2.5 patients/month accumulated over 15 centers
- Accrual period = 36 months
- Follow-up period after the end of accrual = 24 months
- Assumed survival time distribution = Weibull with accelerating hazard and proportional hazards

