10.2 Sample Size Determination

To assess sample size requirements for detecting an improvement in median overall survival (OS) in the experimental treatment arm relative to the historical control arm, we initially assumed 60 to 90 patients receiving standard treatment and follow-up between 1-2016 and 5-2019 would be available for chart review. We assumed that these historical control patients would have a maximum follow-up time of 60 months. For the experimental treatment, we assumed an accrual rate of 2.5 patients per month across 15 participating centers and an accrual period of 36 months, yielding an enrollment of 90 patients in the experimental arm. The patients in the experimental arm would be followed for an additional 24 months after the end of accrual. We considered improvements in median survival ranging from 4 to 8 months to be of clinical interest. We also assumed that survival times would follow a Weibull distribution with proportional hazards and an accelerating hazard function (shape parameter $k=2.0$, estimated from Figure 3A in Eckel-Passow et al [12]. We also considered a more slowly accelerating Weibull shape parameter of $k=1.8$. Under these assumptions, the power to detect **improvements** in median OS using a one-sided log-rank test (one-sided $\alpha=0.05$) are summarized in Table 10 for selected combinations of historical control sample size, Weibull shape parameter, and number of months improvement in median OS [detectable effect size methodology adapted from (Wu and Xiong, 2014)]. We then explored the effect of mixing historical and contemporaneous controls in select mixtures into a single control arm, noting a very slight improvement in power to detect improvements in survival. Overall, a control arm sample size of 90 patients, in historical/contemporaneous control mixtures of 90+0, 80+10, 70+20, and 60+30 all have at least 80% power to detect improvements in survival between 6 and 8 months.

TABLE 10: POWER TO DETECT M MONTHS IMPROVEMENT IN MEDIAN OVERALL SURVIVAL UNDER SELECTED SCENARIOS

Accrual rate (N/mo)	Accrual period (mos)	Follow-up period (mos)	Trial N	Hx Ctl+ Contemp N	Weibull shape k	Power to detect M months improvement in median OS at one-sided $\alpha=0.05$ using the log-rank test				
						M = 4	5	6	7	8
2.5	36	24	90	50+ 0	2.0	0.525	0.667	0.782	0.866	0.922
2.5	36	24	90	60+ 0	2.0	0.565	0.711	0.823	0.899	0.946
2.5	36	24	90	70+ 0	2.0	0.598	0.745	0.853	0.922	0.962
2.5	36	24	90	80+ 0	2.0	0.626	0.773	0.876	0.938	0.972

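### Table 12 counts contemporaneous controls in the chemotherapy-related SAE stopping rule, but section 9.5 collects no adverse events from them, so the rule as written loses sensitivity

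*Combined protocol and SAP*

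**What the plan says.** Section numbers here are those of the protocol body; the table of contents runs one higher.

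- **Section 10.4, stopping rule.** Enrolment halts for evaluation when the cumulative number of patients with an SAE "is equal to or exceeds the relevant boundary indexed by the number of patients currently enrolled". The maximum acceptable chemotherapy-related rate is 50%, and the overall probability of early stopping is set at 0.05.
- **Section 10.4, Table 12 heading.** The boundary is built for 90 treatment-arm patients and "will be expanded to include contemporaneous controls if enrolled".
- **Section 9.5.** Control data come from chart review. The list of items has no safety item, and the text adds: "Adverse Events are not collected, and not reportable for control patients".
- **Section 8.3.5.** "Study Staff will record all reportable events with start dates occurring any time after the start of study treatment". Nothing there extends event recording to the control cohort, which section 9 describes as data collection only.
- **Section 10.1.** The control arm is an "expected mixture ranging between 80 historical controls and 10 contemporaneous controls to 60 historical controls and 30 contemporaneous controls", so contemporaneous controls are expected to enrol.
- **Number treated.** The synopsis sets a goal of "100 interventional subjects and up to 100 historical and contemporaneous control subjects", and section 4.1.2 describes a "study of 100 patients with newly diagnosed high-risk Grade II and III astrocytoma combining TTFIELDS with adjuvant temozolomide". Section 10.2 assumes accrual "yielding an enrollment of 90 patients in the experimental arm", and Tables 11 and 12 both end at patient 90.

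**The concern.** The rule compares a count of patients with an SAE against a boundary indexed by the number of patients enrolled. Both must refer to the same patients. Once contemporaneous controls enter the index while their SAEs go unrecorded, the denominator grows and the numerator cannot. SAEs are a subset of adverse events, so the exclusion in section 9.5 covers them, and the general SAE reporting duty in section 8.3.7 does not mention controls.

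At stake is the stated operating behaviour of one pre-specified safety rule. Under an excessive chemotherapy-related SAE rate in treated patients, the halt would come later or not at all.

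**Working it through.** **1. Reproduce Table 12.** Inputs from section 10.4: acceptable rate 0.50, N = 90, overall crossing 0.05. A Pocock-type boundary with a constant tail takes, at each n, the smallest r with P(X ≥ r | n, 0.5) ≤ a. With a = 0.01003, which is P(X ≥ 23 | 32, 0.5), all 90 printed entries are reproduced. Exact recursion over patients 1 to 90 gives an overall crossing probability of 0.0500. The printed table is correct for 90 treated patients, with these halt probabilities:

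| True rate | 45% | 50% | 65% | 70% |
|---|---|---|---|---|
| P(halt) | 0.0125 | 0.050 | 0.79 | 0.96 |

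**2. What one event-free control does.** From patient 7 to patient 90 the boundary rises at 50 of 83 steps and is flat at 33. Each added patient therefore raises the boundary by about 50/83 = 0.6 on average. A control contributes this increase and no event.

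**3. Extend the boundary.** The expanded table is not printed, so I assume the same method, recalibrated to at most 0.05, for 90 + C patients with C = 10, 20, 30 (section 10.1). The tails are 0.0096, 0.0092 and 0.0084, and the overall crossings are 0.0496, 0.0500 and 0.0499. The final boundary moves from 57 to 63, 68 and 74. All events must come from the 90 treated patients, so the observed treated rate needed at the last look moves from 57/90 = 63.3% to 63/90 = 70.0%, 68/90 = 75.6% and 74/90 = 82.2%.

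**4. Halt probability with event-free controls.** This is an exact recursion over (controls enrolled, SAEs), with controls contributing zero events.

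| Order of controls | True treated rate | C = 10 | C = 20 | C = 30 |
|---|---|---|---|---|
| Random | 50% | 0.011 | 0.0035 | 0.0015 |
| Random | 65% | 0.38 | 0.10 | 0.02 |
| Random | 70% | 0.72 | 0.31 | 0.07 |
| Evenly spaced | 65% | 0.34 | 0.06 | 0.002 |
| Evenly spaced | 70% | 0.70 | 0.24 | 0.02 |
| All first | 70% | 0.63 | 0.16 | 0.008 |
| All last | 70% | 0.96 | 0.96 | 0.96 |

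Five controls in random order already give 0.59 at 65% and 0.88 at 70%. Carrying the tail of 0.01003 forward without recalibrating changes little: 0.73, 0.32 and 0.08 at 70% in random order.

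**5. If control SAEs were collected.** With the same 70% rate in controls, the expanded rule gives 0.975, 0.985 and 0.990, so nothing is lost.

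**6. With 100 treated patients.** Without controls, the recalibrated rule halts with probability 0.82 at 65% and 0.975 at 70%. With 10, 20 or 30 event-free controls in random order, this falls to 0.46, 0.14, 0.04 at 65% and 0.81, 0.41, 0.12 at 70%.

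**7. Patients 91 to 100.** Neither table prints a boundary for them. Table 11 (rate 0.25, N = 90) is also fully reproduced, with crossing 0.0486. The missing entries for both tables are given with the fix.

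**The case against.** The strongest reply is that the loss depends on one reading. A boundary on patients experiencing an SAE could imply that control SAEs would be obtained, and section 11.1.6 has the DSMB assess safety data on each arm. On that reading step 5 applies and nothing is lost. This stands as a limit on the size of the effect, but it does not remove the conflict, because section 9.5 says the opposite and no other section provides the collection.

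Second, timing. The amendment history dates the control cohort to 16 December 2019, about seven months after the first IRB approval on 20 May 2019. At the planned 2.5 patients per month, about 17 treated patients could precede any control. With controls in random order after patient 17, the halt probabilities are 0.45, 0.25, 0.19 at 65% and 0.77, 0.49, 0.35 at 70%. With controls starting only after 45 treated patients, they are 0.85, 0.76, 0.73 at 70%. The near-zero figures therefore depend on early controls, although a material loss remains against 0.79 and 0.96.

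Third, the documents give no chemotherapy-related SAE rate, so 65% and 70% are illustrative. At 45% the printed rule halts with probability only 0.0125, and the practical difference is negligible.

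Fourth, other safeguards remain. A crossing triggers evaluation, not automatic termination. SAEs in treated patients reach the Coordinating Center within 24 hours, the DSMB reviews the data, and Table 11 does not include controls. These limit the severity but do not restore the rule's stated behaviour.

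Two details also weaken any wider claim. Controls do receive adjuvant temozolomide as standard care, and their date of death is collected, though without attribution. Section 9.5 alone carries the point.

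**Conclusion.** The concern holds. Section 10.4 (Table 12) and section 9.5 cannot both be followed as the rule intends, and the only direction in which event-free controls can move the rule is towards lower sensitivity. The size is conditional on three things: that controls are counted without events, how many enrol (10 to 30 expected), and when. At an assumed true treated rate of 70%, the halt probability of 0.96 becomes 0.72, 0.31 or 0.07 with 10, 20 or 30 controls in random order. Across enrolment orders, the 30-control figure ranges from 0.008 to 0.96. The expanded boundary is not printed and is assumed to follow the method that reproduces Table 12. This should be fixed, but it leaves the primary analysis and the device-related rule untouched.

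**What to change.** **Preferred.** In section 10.4, delete the clause "will be expanded to include contemporaneous controls if enrolled" and state that the index is the number of interventional patients enrolled. Printed Table 12 then holds as it stands for 90 interventional patients. In the same edit, correct the Table 12 footnote, which says device-related where the table concerns chemotherapy-related SAEs. The cost is wording only, with no new data. What is given up is a pooled view of chemotherapy-related SAEs across treated patients and contemporaneous controls.

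**Reconcile 90 with 100.** If 100 interventional patients are kept, print both boundaries to 100. The entries for patients 91 to 100 are:

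| Table | Method | Entries 91 to 100 | Crossing |
|---|---|---|---|
| 12 | Printed tail carried on | 58, 58, 59, 59, 60, 60, 61, 61, 62, 63 | 0.052 |
| 12 | Recalibrated to at most 0.05 | 58, 58, 59, 59, 60, 60, 61, 62, 62, 63 | 0.0496 |
| 11 | Printed tail carried on | 34, 34, 34, 35, 35, 35, 35, 36, 36, 36 | 0.0508 |
| 11 | Recalibrated to at most 0.05 | 34, 34, 34, 35, 35, 35, 36, 36, 36, 36 | 0.0499 |

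Recalibrating also raises the Table 12 entries at patients 19, 32, 42, 54 and 82 by one, and the Table 11 entry at patient 22 from 11 to 12.

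**Alternative, at higher cost.** Collect chemotherapy-related SAEs in consented contemporaneous controls, say so in section 9.5, and print the expanded boundary. This changes section 9.5, the eCRF, the control consent form and Table 12. Pooling would still dilute the rule if controls had a lower rate: with treated patients at 65%, controls at 50% and controls evenly spaced, the halt probability is 0.74, 0.70 or 0.65 with 10, 20 or 30 controls, against 0.79 for treated patients alone.
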